3 ETHICAL CONSIDERATIONS

3.1 Good Clinical Practice

This study will be conducted in accordance with Good Clinical Practice (GCP), as defined by the International Conference on Harmonisation (ICH) and in accordance with the ethical principles underlying European Union Directive 2001/20/EC and the United States Code of Federal Regulations, Title 21, Part 50 (21CFR50).

The study will be conducted in compliance with the protocol. The protocol, any amendments, and the subject informed consent will receive Institutional Review Board/Independent Ethics Committee (IRB/IEC) approval/favorable opinion before initiation of the study.

All potential serious breaches must be reported to Bristol-Myers Squibb (BMS) immediately. A serious breach is a breach of the conditions and principles of GCP in connection with the study or the protocol, which is likely to affect, to a significant degree, the safety or physical or mental integrity of the subjects of the study or the scientific value of the study.

Study personnel involved in conducting this study will be qualified by education, training, and experience to perform their respective tasks.

This study will not use the services of study personnel where sanctions have been invoked or where there has been scientific misconduct or fraud (eg, loss of medical licensure; debarment).

3.2 Institutional Review Board/Independent Ethics Committee

Before study initiation, the investigator must have written and dated approval/favorable opinion from the IRB/IEC for the protocol, consent form, subject recruitment materials/process (eg, advertisements), and any other written information to be provided to subjects. The investigator or sponsor should also provide the IRB/IEC with a copy of the Investigator Brochure or product labeling information to be provided to subjects, and any updates.

The investigator should provide the IRB/IEC with reports, updates, and other information (eg, expedited safety reports, amendments, and administrative letters) according to regulatory requirements or institution procedures.

3.3 Informed Consent

Investigators must ensure that subjects are clearly and fully informed about the purpose, potential risks, and other critical issues regarding clinical studies in which they volunteer to participate.

Investigators must:

- 1) Provide a copy of the consent form and written information about the study in the language in which the subject is most proficient prior to clinical study participation. The language must be non-technical and easily understood.
- 2) Allow time necessary for subject to inquire about the details of the study.
- 3) Obtain an informed consent signed and personally dated by the subject and by the person who conducted the informed consent discussion.
- 4) Obtain the IRB/IEC's written approval/favorable opinion of the written informed consent form and any other information to be provided to the subjects, prior to the beginning of the study, and after any revisions are completed for new information.
- 5) Revise the informed consent whenever important new information becomes available that is relevant to the subject's consent. The investigator, or a person designated by the investigator, should fully inform the subject of all pertinent aspects of the study and of any new information relevant to the subject's willingness to continue participation in the study. This communication should be documented.
- 6) Reconsenting of patients can be done in person or, if the patient is unable to re-consent in person, over the phone. If the re-consent is required to be performed over the phone, the coordinator will send an updated consent form to the patient via mail or electronically. When the patient has received the consent, the coordinator will review the consent with the patient over the phone. Any questions can be answered by the coordinator during the consenting process. The patient will then send the original signed consent back to the coordinator. The coordinator who conducted the phone consent will sign and date the applicable line and upload to the patient's chart. The coordinator must also document the consent discussion and receipt of the consent in the patient's EMR.

The rights, safety, and well-being of the study subjects are the most important considerations and should prevail over interests of science and society.

4 INVESTIGATIONAL PLAN

4.1 Study Design and Duration

Planned study design: prospective, controlled, randomized pilot study

Screening procedures/study population: Patients will be eligible for screening if they develop atrial fibrillation in the postoperative period that:

1. Persists 12 hours or more.
2. Develop recurrent atrial fibrillation with two or more episodes of persistent AFib of at least 30 minutes duration during the same hospital stay.

Number of subjects per arm: 28

Randomization ratio/method: 1:1, determined in permuted block fashion

Duration of treatment: 30 days of oral anticoagulation therapy. This period will start with the first dose of anticoagulation (either apixaban or warfarin) given in the hospital, and continue until the patient's 30-day post-operative appointment.

Criteria for evaluation:

- Efficacy: systemic thromboembolism or stroke will be assessed retrospectively after the patient has completed the 30-day course of therapy.
 - Events relating to thromboembolism or stroke will be adjudicated using pre-determined definitions by independent committee members that remain blinded to the patient's treatment arm.
- Safety: major bleeding will be as defined by the Society on Thrombosis and Haemostasis, as follows:
 - 1. Fatal bleeding, and/or
 - 2. Symptomatic bleeding that occurs in a critical area or organ, such as intracranial, intraspinal, intraocular, retroperitoneal, pericardial, in a non-operated joint, or intramuscular with compartment syndrome, assessed in consultation with the surgeon, and/or
 - 3. Extrasurgical site bleeding causing a fall in hemoglobin level of 20 g/L (2g/dL) or more, or leading to transfusion of two or more units of whole blood or red cells within 24-48 hours of the bleeding and/or
 - 4. Surgical site bleeding that requires a second intervention – open, arthroscopic, endovascular- or a hemarthrosis of sufficient size as to interfere with rehabilitation by delaying mobilization or delayed wound healing, resulting in prolonged hospitalization or a deep wound infection, and/or
 - 5. Unexpected surgical site bleeding, prolonged and/or sufficiently large to cause hemodynamic instability, as assessed by the surgeon, with a fall in hemoglobin of at least 20 g/L (2g/dL) or transfusion of two or more units of whole blood or red cells within 24 hours of the bleeding.³

In the hospital, bleeding will be assessed daily by monitoring hemoglobin and the need for transfusions. After discharge and until the patient's 30-day post-operative evaluation, we will monitor for readmissions related to bleeding, indicated by the need for transfusion of at least two units of blood products. Any patient phone calls that already occur as part of routine post-operative care will continue; however, there are no additional post-discharge phone calls to the patient related to this study.

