
Data Analysis Plan
	
Efficacy and safety data will retrospectively assessed and analyzed after the patient has completed the 30-day course of therapy. Events relating to thromboembolism or stroke will be adjudicated using pre-defined endpoint definitions by independent committee members that remain blinded to treatment arm. Safety events, including major bleeding will be as defined by the International Society on Thrombosis and Haemostasis.³ In the hospital, bleeding will be assessed daily by monitoring hemoglobin and the need for transfusions, and defined by a drop in hemoglobin of > 2 gm/dL in the previous 24 hours, or transfusion of at least two units of blood products. After discharge, we will monitor for readmissions related to bleeding, indicated by the need of transfusion of at least two units of blood products.

Statistics:
	
Continuous variables will be expressed as mean ± standard deviation or median with interquartile range (IQR) as appropriate. Continuous variables will be compared using t-tests for parametric data or Wilcoxon analysis for nonparametric data. We will complete the analysis in an intent-to-treat manner. We will include analysis for confidence intervals and other appropriate statistical tests to assess binary outcomes. We realize that statistical comparison between groups will be of limited utility in this pilot study as this study is not powered for comparison of events between groups. Data will be analyzed using JMP software, version 12.0.0 (Cary, NC).

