1 INTRODUCTION

Apixaban is a novel, orally active, potent, direct selective inhibitor of coagulation FXa that directly and reversibly binds to the active site of FXa and exerts anticoagulant and antithrombotic effects by diminishing the conversion of prothrombin to thrombin. Apixaban is currently indicated to reduce stroke and systemic embolism in patients with nonvalvular atrial fibrillation, for the treatment of deep venous thrombosis (DVT), and for the prophylaxis of DVT in patients who have undergone hip or knee replacement surgery. Apixaban is not indicated for the treatment of atrial fibrillation caused by valvular heart disease or for patients with mechanical prosthetic valves requiring chronic oral anticoagulation.

Patients undergoing coronary artery bypass grafting (CABG) are at risk for the development of postoperative atrial fibrillation (POAF). POAF adversely impacts patient outcomes, and patients who develop POAF are at increased risk for stroke or thromboembolic complications, with an increased duration of hospitalization. Usually occurring in the early postoperative period and usually short-lived, POAF requires anticoagulation when persistent or recurrent. Duration of therapy for POAF is typically short-term, as POAF is usually short-term and self-limiting over 3-4 weeks.

Warfarin therapy has been the mainstay of therapy for patients with POAF. While the duration of therapy is usually short (3-4 weeks), complications of anticoagulation do occur. Additionally, warfarin therapy for POAF is associated with increased length of stay, need for monitoring, and bleeding complications.

Apixaban has been demonstrated to be superior to warfarin for the reduction of stroke or systemic embolism in patients with non-valvular atrial fibrillation. Additionally, major bleeding was significantly reduced in patients receiving apixaban compared to warfarin. The use of apixaban in patients with POAF has not been well studied, however, and whether these benefits will be seen in patients with POAF is unclear. In this small prospective pilot study, we aim to compare apixaban and warfarin anticoagulation strategies for the outcomes of venous thromboembolism/stroke and bleeding events when utilized in patients with new-onset postoperative atrial fibrillation after isolated coronary artery bypass grafting (CABG).

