2 STUDY OBJECTIVES

2.1 Primary Objective

- 1) Efficacy: Venous thromboembolism or stroke, followed until postoperative day 30.
- 2) Safety: major and minor bleeding events, followed until postoperative day 30, as defined by the International Society on Thrombosis and Haemostasis³
- 3) Clinical relevant non-major bleed.
- 4) Transfusions: units of blood or blood products given after the first dose of anticoagulation.
- 5) Total post-operative length of stay in days, defined as the time the patient leaves the operating room (day 0) until hospital discharge. Length of stay will increase by 1 day with each midnight that is passed.
- 6) Time in therapeutic range of INR, if on warfarin, (eg. 2-3), measured as a percentage and defined for each patient using the Rosendaal equation.
- 7) Patient compliance percentage to apixaban dosing, calculated as a percentage using the following equation
 - a. $(\# \text{ doses prescribed} - \# \text{ of doses not taken and returned to investigator at follow up appointment}) / \# \text{ doses prescribed}$; the follow up visit will occur after anticoagulation prescription has ended.

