6.3 Safety Assessments

1) Major bleeding, as defined by the International Society on Thrombosis and Haemostasis based on the following criterion:

- a. Fatal bleeding, and/or
- b. Symptomatic bleeding that occurs in a critical area or organ, such as intracranial, intraspinal, intraocular, retroperitoneal, pericardial, in a non-operated joint, or intramuscular with compartment syndrome, assessed in consultation with the surgeon, and/or
- c. Extrasurgical site bleeding causing a fall in hemoglobin level of 20 g/L (2g/dL) or more, or leading to transfusion of two or more units of whole blood or red cells within 24-48 hours of the bleeding and/or
- d. Surgical site bleeding that requires a second intervention – open, arthroscopic, endovascular- or a hemarthrosis of sufficient size as to interfere with rehabilitation by delaying mobilization or delayed wound healing, resulting in prolonged hospitalization or a deep wound infection, and/or
- e. Unexpected surgical site bleeding, prolonged and/or sufficiently large to cause hemodynamic instability, as assessed by the surgeon, with a fall in hemoglobin of at least 20 g/L (2g/dL) or transfusion of two or more units of whole blood or red cells within 24 hours of the bleeding.³

2) Clinical relevant non-major bleed, defined as any notable bleeding not classified as major.

3) Pregnancy tests will be performed pre-operatively on the day of surgery for all WOCBP, via urine hCG screening.

4) A baseline renal function panel will be obtained either pre-operatively or within 30 days of surgery. The renal function panel includes: glucose, BUN, creatinine, BUN/creatinine ratio, sodium, potassium, bicarbonate, chloride, calcium, phosphorus, albumin, and anion gap.

5) The hepatic function test panel will be ordered before initiating warfarin (if a recent baseline is not available). This panel includes: total protein, albumin, alk phos, AST, ALT, total bilirubin, direct bilirubin, and indirect bilirubin.

6) INR will be checked before surgery to ensure the patient's INR is within normal limits in preparation for their surgery, regardless of whether they were previously on warfarin, and again upon initiation of warfarin therapy. INR will be checked daily in the hospital, and at each visit to the anticoagulation clinic. These visits are usually scheduled within three days of discharge from the hospital, then twice weekly until the INR is therapeutic, then weekly for the duration of the study.

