6.4.2 Secondary Assessments

- 1) Units of blood or blood products given after the first dose of anticoagulation.
- 2) Total post-operative length of stay: This will be measured from the date/time of the end of the subject's surgery until the date/time of the patient's discharge from the hospital. This will be measured in hours, to the nearest tenth of an hour.
- 3) Duration from diagnosis of post-operative atrial fibrillation (POAF) to discharge from the hospital: This will be measured from the time of the EKG that is obtained after AFib is noted on telemetry (confirming the diagnosis of AFib), until hospital discharge. This will be measured in hours, to the nearest tenth of an hour.
- 4) Time in therapeutic range of INR, if on warfarin, (eg. 2-3), measured as a percentage and defined for each patient using the Rosendaal equation
- 5) Patient compliance percentage to apixaban: measured by asking the patient to bring any unused medication to their 30-day post-operative appointment, where remaining tablets will be counted. This will be calculated as a percentage using the following

equation: (# doses prescribed - # of doses not taken and returned to investigator at follow up appointment) / # days prescribed.

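### Bleeds recognised by a hemoglobin fall are easier to detect before discharge; if warfarin patients stay longer, as the protocol expects, the raw bleeding comparison leans modestly toward apixaban

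*Combined protocol and SAP*

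**What the plan says.** **Before discharge.** Section 4.1: "In the hospital, bleeding will be assessed daily by monitoring hemoglobin and the need for transfusions". The synopsis (Data Analysis Plan) adds that an in-hospital bleed is "defined by a drop in hemoglobin of > 2 gm/dL in the previous 24 hours, or transfusion of at least two units of blood products".

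**Once the patient has left hospital.** Section 4.1: "we will monitor for readmissions related to bleeding, indicated by the need for transfusion of at least two units of blood products", and "there are no additional post-discharge phone calls to the patient related to this study". The Time and Events Schedule in 6.1 has no hemoglobin row, and the renal and hepatic panels listed in 6.3 do not include it. The schedule does mark bleeding monitoring at the 30-day examination, and at anticoagulation clinic visits in a column labelled for warfarin.

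**What is counted.** Section 2.1 lists "major and minor bleeding events, followed until postoperative day 30". The major bleeding definition in 4.1 and 6.3 includes "Extrasurgical site bleeding causing a fall in hemoglobin level of 20 g/L (2g/dL) or more".

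**Length of stay.** The Introduction states that "warfarin therapy for POAF is associated with increased length of stay, need for monitoring, and bleeding complications". Section 6.4.2 makes length of stay a secondary assessment, together with "Duration from diagnosis of post-operative atrial fibrillation (POAF) to discharge from the hospital".

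**Analysis.** Section 9.3 offers confidence intervals and unspecified appropriate tests for binary outcomes. It says nothing about days under hemoglobin monitoring. Blinded adjudication is described for thromboembolism and stroke, not for bleeding.

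**The concern.** A fall in hemoglobin is seen only where hemoglobin is measured. The plan measures it daily up to discharge and schedules none afterwards, although the outcome runs to day 30. Discharge comes after randomization in an open-label trial, and the protocol expects warfarin to delay it. The time during which this type of bleed can be recognised may therefore differ by arm because of the treatment itself, so randomization does not balance it.

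Bleeding is half of the research hypothesis, and section 1.2 hopes for a signal of benefit and safety. If more hemoglobin-fall bleeds are found on warfarin only because those patients were watched longer, that signal would pass uncorrected into the later studies that section 9.1 says this pilot should inform.

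**Working it through.** **The plan's own figures.** No bleeding rate, power or length-of-stay figure is given, so there is none to reproduce. The feasibility numbers in 9.1 hold: 300 × 0.25 × 0.95 = 71.25 against the stated 70, and 2 per month × 28 months = 56. They do not bear on this point.

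**Inputs from the documents.** 28 patients per arm (4.1); follow-up to postoperative day 30 (2.1); longer stay on warfarin, number of days not stated (Introduction).

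**Assumptions.** True risk of this type of bleed is equal in both arms, 10% to 20%. There are W = 27 days from first dose to day 30. In-hospital days on drug are d = 3 or 4 on apixaban and 1 to 3 more on warfarin. A share s of these bleeds is still found after discharge. The hazard h is constant.

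**Formula.** h = −ln(1 − true risk)/W. Detected risk = 1 − exp(−h × [d + s × (W − d)]).

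**Worked example at 10% true risk.** h = −ln(0.90)/27 = 0.0039.

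- s = 0, 3 versus 6 days: 0.0116 and 0.0231, ratio 1.99, difference 28 × (0.0231 − 0.0116) = 0.32 events.
- s = 0.5, 3 versus 4 days: effective days are 3 + 0.5 × 24 = 15 and 4 + 0.5 × 23 = 15.5. Risks are 0.0569 and 0.0587, ratio 1.03, difference 0.05 events.

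**Range over the assumptions** (detected risk ratio, warfarin to apixaban; extra detected events per 28 in parentheses):

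| Extra warfarin days | s = 0 | s = 0.25 | s = 0.5 |
|---|---|---|---|
| 1 | 1.24–1.33 (0.11–0.22) | 1.07–1.08 (0.08–0.16) | 1.03 (0.05–0.10) |
| 3 | 1.73–1.99 (0.32–0.67) | 1.22–1.24 (0.24–0.48) | 1.09–1.10 (0.15–0.30) |

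With equal stays, or with s = 1, the ratio is 1.00.

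**Front-loaded hazard.** With a half-life of 3 or 7 days, 10% true risk and 3 base days, 1 to 3 extra days give 1.20–1.72 at s = 0 and 1.06–1.16 at s = 0.5. The direction is unchanged.

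**Cross-check with a simpler count.** Expected detected events are 28 × (1 − (1 − q)^d), with a daily detection probability q of 0.5% to 1% and nothing found after discharge. Matched scenarios differ by 0.14 events (q = 0.5%, 3 versus 4 days: 0.42 and 0.56) up to 0.81 (q = 1%, 3 versus 6 days: 0.83 and 1.64).

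**Would a rate per in-hospital day correct it?** Take identical front-loaded risk, 3 versus 6 in-hospital days and s = 0.

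- Half-life 3 days: the shares of total hazard falling in hospital are 0.501 and 0.751. The rate ratio is (0.751/6)/(0.501/3) = 0.75.
- Half-life 7 days: 0.276 and 0.481, giving (0.481/6)/(0.276/3) = 0.87.

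Both are below 1, so this correction would make warfarin look safer when risk is equal. It also conditions on a discharge that bleeding itself can delay.

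**The case against.** **The size is assumed.** This stands. The expectation of a longer stay is one background sentence with no number of days. A reader might infer that the comparison is tilted as a matter of fact, or that any apixaban safety advantage would be an artefact. The documents support only a conditional statement, and the upper ratios require that no such bleed is found after discharge.

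**Surveillance does not stop at discharge.** This stands in part. A reader might infer that only readmissions are watched. But 6.1 marks bleeding monitoring at the 30-day examination for everyone, non-serious adverse events are collected from the start of study drug (7.2.1), serious ones to 30 days after dosing ends (7.1.1), and clinically significant laboratory abnormalities are captured (7.3). So s is probably above zero. None of these schedules a hemoglobin, however, and the clinic visits labelled for warfarin would add contact in the same arm.

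**Minor bleeds are not affected in the same way.** Correct. Section 6.3 defines the non-major category as any notable bleeding not classed as major, which needs no hemoglobin result. The point should not be extended to it.

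**The definition narrows the exposure.** This stands in part. Sections 4.1 and 6.3 require a bleed that causes the fall, or an unexpected surgical-site bleed with hemodynamic instability; a laboratory drop alone suffices only under the synopsis wording. Which wording governs is a separate question, but the size of the effect depends on it.

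**It is an unpowered pilot, and 9.3 does not name bleeding among the binary outcomes.** True, and this lowers the consequence. Low power concerns precision, though, and does not remove a directional detection difference.

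**Conclusion.** The point holds as a conditional and modest detection bias. The documents establish that hemoglobin monitoring is daily until discharge and unscheduled after it, that the outcome runs to day 30, that a hemoglobin fall can make a bleed major, that warfarin is expected to lengthen stay, and that 9.3 makes no allowance for this. Given a longer warfarin stay and incomplete detection after discharge, the direction is against warfarin in every scenario examined.

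Under a constant hazard, equal true risk of 10% to 20%, 3 to 4 in-hospital days on apixaban and 1 to 3 more on warfarin, the spurious ratio is about 1.03 to 1.99. In events it is below one per 28 patients in every calculation: 0.05 to 0.67 in the main model and up to 0.81 in the simpler count. It is zero if stays are equal. Fatal, critical-site and re-intervention bleeds should be found in either setting. This does not threaten the trial, but with so few events expected it is worth settling before the data are read.

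**What to change.** Amend section 9.3 as follows.

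1. Keep the full ISTH bleeding result by arm.
2. Add a pre-specified between-arm comparison limited to bleeds that do not depend on routine hemoglobin: fatal, critical-site, re-intervention, and transfusion of two or more red-cell units. Note that the transfusion criterion is only nearly neutral, because daily hemoglobin can prompt a transfusion in hospital, whereas after discharge a transfusion is sought through readmission.
3. Report bleeds that qualify by hemoglobin fall alone separately by arm, beside the number of hemoglobin-monitored days after first dose in each arm.
4. Add a companion analysis in a common early window from first dose. Fix its length without reference to outcomes by arm, and make it short enough that nearly all patients in both arms are still in hospital.
5. State that a difference in hemoglobin-fall-only bleeds will not by itself be read as a drug effect.
6. Do not use a rate per in-hospital patient-day as the correction.

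The cost is SAP wording, one derived variable from dates already in the medical record, and a little more analysis. Treatment, visits and sample size are unchanged. The downside is fewer events in the restricted comparison, hence wider intervals, and the early window says nothing about later bleeds.
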